7.3 FOLLOW-UP

If patients miss two peer mentoring sessions in a row and have not responded to other program communications, UM staff will contact their clinic in an attempt to reach them to determine if they want to continue in the program (see "Recruitment and Retention Procedure Final").

Study outcomes will be monitored in all facilities for 12 weeks after the 24-week intervention period. The same routinely-collected data from FMCNA will be collected during this period. This is a pragmatic clinical trial and therefore no special follow-up will occur as a result of the study.

7.4 FINAL STUDY VISIT

N/A

7.5 EARLY TERMINATION VISIT

N/A

7.6 UNSCHEDULED VISIT

N/A

8 STUDY PROCEDURES/EVALUATIONS

8.1 CLINICAL EVALUATIONS

Routine dialysis care will continue throughout the study but may be influenced by the provider intervention training and IDH checklist, and by the peer mentoring if patients begin to engage more in fluid management. Please refer to previous section on interventions regarding the provider training, IDH Checklist and peer mentoring. Data from FMCNA are routinely gathered as part of this routine care. The only change to the usual clinical evaluation is that two aforementioned extra questions will appear in the Chairside documentation system once per week during the study period: (1) the question about patients' post-dialysis recovery time; and (2) the question in which the FMCNA staff member records whether the patient made a request that day about their fluid removal goal.

8.2 LABORATORY EVALUATIONS

8.2.1 Clinical Laboratory Evaluations

Routine dialysis care will continue throughout the study. No changes to usual laboratory evaluations are expected.

8.2.2 Special Assays or Procedures

N/A

8.2.3	Specimen Preparation, Handling, and Shipping
N/A	8.2.3.1 Instructions for Specimen Preparation, Handling, and Storage
N/A	8.2.3.2 Specimen Shipment

9. ASSESSMENT OF SAFETY

9.1 SPECIFICATION OF SAFETY PARAMETERS

Intradialytic hypotension is the primary study outcome.

9.2 METHODS AND TIMING FOR ASSESSING, RECORDING, AND ANALYZING SAFETY PARAMETERS

9.2.1 Adverse Events

This study has low risk to patients. The study uses current, accepted ways to reduce low blood pressure during dialysis.

9.2.2 Expected Adverse Reactions

There are no expected adverse reactions to the interventions.

9.2.3 Serious Adverse Events

This study has low risk to patients. The study uses current, accepted ways to reduce low blood pressure during dialysis.

9.2.4 Unanticipated Problems

This study has low risk to patients. The study uses current, accepted ways to reduce low blood pressure during dialysis.

9.2.5 Procedures to be Followed in the Event of Abnormal Laboratory Test Values or Abnormal Clinical Findings

This study has low risk to patients. The study uses current, accepted ways to reduce low blood pressure during dialysis.

9.3 REPORTING PROCEDURES

Adverse events (AEs) other than potential breach of confidentiality will not be systematically collected since this is an educational intervention that provides content on current, accepted

ways to reduce low blood pressure during dialysis. Thus the risk profile for such approaches is well known, and the risk to patients is very low.

Non-confidentiality-related AEs will also not be systematically tracked since the hemodialysis patient is very ill at baseline. Most patients have multiple chronic diseases, including cardiovascular disease. Approximately 15-20% of hemodialysis patients die per year and the patient population has an average of two hospitalizations per patient year. The primary outcome, intradialytic hypotension (IDH), occurs in 20% of hemodialysis sessions in the United States. More than 50% of patients experience symptoms during or shortly after hemodialysis. These data (mortality, hospitalizations, IDH, and symptoms) are tracked as outcomes in our study; these events occur routinely in the hemodialysis population and thus these events would be expected without our study, thus making “relatedness” of these events to the study exceedingly difficult to determine. These outcomes will be collected between two months and two years from the occurrence based on the data source available.

- ***The only expected risk for this study is of breach of confidentiality. The likelihood of this risk is very low and unexpected because of the confidentiality measures outlined in section 14.5 II. However, in the unlikely event that there were an adverse event related to breach of confidentiality, this would be reported to the IRB using the following generalized rating scale:*** 0 - No adverse event
- 1 - Mild AE – No treatment needed
- 2 - Moderate AE – Resolved with treatment
- 3 - Severe AE – Inability to carry on normal activities, required professional medical attention
- 4 - Life-threatening or disabling AE
- 5 - Fatal AE

While breach of confidentiality is extremely unlikely and if it were occur it would be unlikely to be severe, if needed, we would nonetheless report any serious AEs according to the following typology:

- Death
- A life-threatening adverse drug experience
- Inpatient hospitalization or prolongation of existing hospitalization
- A persistent or significant disability/incapacity
- A congenital anomaly/birth defect
- Important medical events that may not result in death, be life-threatening, or require hospitalization may be considered a serious adverse drug experience when, based upon appropriate medical judgment, they may jeopardize the patient or subject and may require medical or surgical intervention to prevent one of the outcomes listed in this definition. Examples of such medical events include allergic bronchospasm requiring

intensive treatment in an emergency room or at home, blood dyscrasias or convulsions that do not result in inpatient hospitalization, or the development of drug dependency or drug abuse.

Potential confidentiality breaches will be tracked as follows by UMSI and UM-KECC:

- A log of data transfers, which will record the transfer's date, time, sender, receiver, data contents, transmission vehicle, a yes/no checkbox identifying whether or not there was a potential confidentiality breach in that transfer, and a free-text box in which to describe the issue. Another free-text box will capture any remedies taken to address the issue (e.g., notifications, data deletion).
- A log of security events, in which any attempted or successful security breaches, their dates/times, involved parties, data accesses, and remedies taken will be recorded. This will include any the details of any hacking attempts or inadvertent disclosures not involving data transfers, which would be captured as per above.

Finally, the PI or a co-investigator will assess the relatedness of any breach of confidentiality to the study according to the following typology:

- Definitely related
- Probably related
- Possibly related
- Unlikely to be related
- Definitely not related.

We will also assess the expectedness of the event, although any breach of confidentiality would be inherently unexpected.

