Peer mentor training. The training manual is adapted from NKF's existing curriculum in consultation with peer mentors and the Advisory Committee. There will be multiple training cycles over the course of the project. Training will be nine hours long, divided into six teleconference based sessions lasting 90 minutes each. Training will include information on (1) the role of the peer mentor, (2) CV stability, (3) listening and communication skills, including MI techniques, (4) sharing experiences and strategies; (5) confidentiality and boundaries, and (5) program protocol/logistics such as using multimedia tools, intervention fidelity and record-keeping (see Figure 1). Peer mentors will be trained to refer patients with obvious symptoms of depression or other mental health issues to NKF staff. Trainers for the peer mentor program training will consist of NKF staff and peer mentors; they will receive recorded training on motivational interviewing (MI) from [name], a leading expert on MI. To ensure mentors have gained needed skills, each mentor will be assessed during role plays. The fidelity of training sessions will be tracked with the use of checklists.

Peer mentor supervision/support. Mentors will receive ongoing support via monthly phone calls from NKF staff. An e-community will be available to peer mentors, developed with input from the focus groups. Within the e-community, peer mentors will have access to a communication tool with which to speak with one another, records of their progress, and educational materials. The e-community will be developed using Basecamp, a collaboration platform already used by NKF volunteers and staff. No patient data will be entered into Basecamp.

Peer mentor motivation and burnout prevention. Current demographics and interest levels in the NKF program shed predictive insight into the future engagement of Dialysafe peer mentors.

Reflecting on NKF statistics from June 2018, we are encouraged by the likelihood of high peer mentor motivation and low mentor burnout.

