The NKF Project Coordinator and the NKF Project Assistant will communicate with all potential/actual mentors and mentees throughout the course of the project on an ongoing basis, utilizing the online platform described above to automate reminders and communications when possible. The Project Coordinator will work with the University of Michigan to develop the online platform and ensure that it meets the needs of the project. The online community will also be a moderated environment in which mentors can access project-related materials and support one another and problem-solve together as they mentor patients as part of the project. This online community is part of our plan for facilitating ongoing learning and feedback among peer mentors.

Emergency procedures (See attachment entitled: *Dialysafe Peer Mentor Emergency Procedures*). In the case that a patient has a medical emergency during a peer mentor **session**, the peer mentor will encourage the patient to call for/get the attention of a clinic nurse. The peer mentor will then end the videoconference; that is, the peer mentor will not continue the Dialysafe project-related discussion once an incident has occurred. The peer mentor will report any incomplete session discussions through the peer mentor view of the Dialysafe peer mentor management system (PMMS), which will be visible to the Peer Mentoring Program Coordinator at the National Kidney Foundation. Interrupted sessions will be rescheduled, if possible.

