In the case that a patient indicates that they may be of danger to themselves or others, peer mentors are obligated to share this information with the Peer Mentoring Program Coordinator at the National Kidney Foundation. Should the program coordinator not be available, there will be a backup coordinator who can be contacted. While peer mentors must keep strict confidentiality with all mentees, the peer mentor training will explicitly state that this rule does not apply to suicidal or homicidal ideation. Mentors who have reason to believe that a mentee is suicidal or homicidal will inform the mentee that they are concerned about them and cannot keep what was shared confidential. The peer mentor will then contact the Peer Mentoring Program Coordinator by email or phone. This will then be followed up by the Peer Mentoring Program Coordinator, who will communicate directly with the mentee about whom the concern was expressed. The mentee will be assessed for suicidal/homicidal ideations and their intentions/plan, as well as an assessment of the patient's support system in place at the time. The mentee will be referred back to their clinic social worker as well. The program coordinator will also be responsible for notifying the clinic manager or designated appointee at the dialysis facility, who in turn will notify the attending physician responsible for the care of the patient.

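### Three event types foreseen in peer mentoring have no visible count or oversight route, and the emergency instruction in section 4.1 relies on a clinic nurse although calls take place away from the clinic

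*Combined protocol and SAP*

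**What the plan says.** Section 9.3 gives the collection rule: "Adverse events (AEs) other than potential breach of confidentiality will not be systematically collected since this is an educational intervention". It offers two reasons. The content is accepted practice for preventing low blood pressure, and these patients are so ill that deaths, admissions, hypotension and symptoms would occur anyway; those four are collected as outcomes. Confidentiality breach is named as the sole expected risk and receives the safety machinery: "Potential confidentiality breaches will be tracked as follows by UMSI and UM-KECC", with two logs, and "the PI or a co-investigator will assess the relatedness of any breach of confidentiality to the study according to the following typology".

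Section 4.1 VIII foresees other events in mentoring. On mental health: "Peer mentors will be trained to refer patients with obvious symptoms of depression or other mental health issues to NKF staff" (section 6.1.2 repeats this). On danger to self or others: "peer mentors are obligated to share this information with the Peer Mentoring Program Coordinator at the National Kidney Foundation", after which the coordinator or a backup follows up with the mentee, who is assessed and referred to the clinic social worker; the clinic manager is told and in turn tells the attending physician. On a medical emergency during a call: "the peer mentor will encourage the patient to call for/get the attention of a clinic nurse". The mentor then ends the video link and reports the incomplete session in the peer mentoring management system (PMMS), where the NKF coordinator can see it.

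Section 6.2.2 puts all modules and video calls in the patient's home or skilled nursing facility.

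**The concern.** The reasons given in section 9.3 concern dialysis events. They say nothing about events that arise or come to light inside a mentoring call. If nobody tallies those, the DSMB and the final report have no number for them, and a reader weighing adoption of peer mentoring cannot tell whether none occurred or none were counted. The waiver of consent requested in section 14.3 rests on minimal risk, and a count would give the IRB and DSMB something to check that premise against.

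The second matter is practical. A mentee who becomes unwell at home is told to get help from someone in another building, and the mentor is told to end the call.

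**Working it through.** This is mainly a check of text against text.

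**1. Follow each event type to its last named recipient.**

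| Event type | Where foreseen | Named recipients | Stated count | Stated route to IRB or DSMB |
|---|---|---|---|---|
| Suicidal or homicidal ideation | 4.1 VIII, emergency procedures | NKF coordinator or backup, clinic social worker, clinic manager, attending physician | None | None |
| Mental-health referral | 4.1 VIII and 6.1.2, mentor training | NKF staff | None | None |
| Call ended for a medical emergency | 4.1 VIII, emergency procedures | NKF coordinator, through the incomplete-session report | None | None |

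So 0 of 3 has a stated count and 0 of 3 a stated route. One of 3, the emergency-ended call, leaves a PMMS record, but the visible text does not say that the reason is recorded.

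**2. Look for another route.** Section 9.2.4 (unanticipated problems) says only that risk is low. Sections 9.3.1, 9.3.4 and 9.3.5 are marked not applicable. Sections 9.6, 11.3 and 15.4 anticipate DSMB reports on hypotension and mortality. Section 15.6 sends protocol deviations to the IRB, not participant events.

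**3. Look for data that could substitute.** Section 6.5 describes records of completed sessions. Section 11.4, Aim 3, counts no-shows and abandoned video sessions without separating causes. Tables 10 and 11 in section 14.5 show sessions completed and missed and mentoring start and stop dates, with no reason field. The kidney disease quality-of-life survey and cause-specific admissions (section 3.2.2) give controlled data on well-being and hospital use, but not these counts.

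**4. Could start and stop dates pick out an emergency linked to a call?** Inputs: section 9.3 says "the patient population has an average of two hospitalizations per patient year"; section 4.1 VIII gives up to 30 mentees in each of 10 clinics, 30 × 10 = 300; section 7 gives 5 to 6 weeks on average. Background admissions in that window are 300 × 2 × 5/52 = 57.7 to 300 × 2 × 6/52 = 69.2. The one-week minimum in section 2.1.1 gives 11.5, and the 12-week upper end of the call script in section 7.2 gives 138.5. This assumes that mentees have the population rate and all stay for the whole window. An admission between those dates therefore does not identify a call-linked emergency. These figures show only that; they do not estimate uncounted events.

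**5. Compare the emergency instruction with the place of the call.** The instruction needs a clinic nurse within reach. Sections 2.1.1, 6.2.2, 6.4 and the call script in 7.2 describe home use, and 6.2.2 and 6.4 add skilled nursing facilities. No visible step has the patient or mentor contact emergency services or nursing-facility staff.

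**6. What a tally would allow.** With zero events among n mentees treated as independent, the one-sided 95% upper bound on risk per mentee is 1 − 0.05^(1/n): 0.99% for n = 300, and 1.49% for n = 200, an assumed shortfall because 30 per clinic is a ceiling.

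**The case against.** The strongest reply is that much of this is already handled. Ideation has a full clinical chain. An incomplete session is reported in the PMMS, to which section 12 gives the principal investigator access. An emergency that leads to admission or death enters the outcome data in every arm, a randomized comparison that a mentoring log cannot offer. The DSMB may ask for more. A referral is a service, and disclosed ideation may be long-standing, so neither is plainly an adverse event. The emergency-procedures attachment, the mentoring fidelity checklists and the incomplete-session form were not available and may already hold a log or a reason field.

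Most of this stands, and it limits the point. A reader might infer that section 9.3 forbids collecting any adverse event. It does not: it says that collection will not be systematic, and four kinds of clinical event are tracked as outcomes. A reader might also infer that a distressed mentee gets no response, or that no log exists. The text contradicts the first and cannot settle the second. Formal rating of relatedness for ideation that may predate mentoring is also debatable.

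The reply does not supply a count. Access to the PMMS is not a tally, and a DSMB request cannot retrieve numbers that nobody keeps.

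On the clinic nurse, section 4.1 VIII still speaks of tablets provided to clinics, and section 15.6 of use during dialysis. The instruction would suit that setting, but section 6.2.2 places all calls elsewhere.

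**Conclusion.** The point holds in a limited form. What is missing from the visible text is research-side counting and oversight of three foreseen event types, not the clinical response to ideation. Its size is 0 of 3 types counted and 0 of 3 routed to the IRB or DSMB, in a group of up to 300 mentees. No event rate is given, so neither harm nor a number of missed events is claimed. The conclusion is conditional on the unseen attachment and forms. The instruction to find a clinic nurse does not work as written for calls placed where section 6.2.2 puts them, unless the attachment overrides it. No primary or secondary efficacy result is affected.

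**What to change.** 1. Amend the emergency procedure in section 4.1 VIII. The patient or mentor contacts 911, or facility staff if the patient is in a skilled nursing facility, and the NKF coordinator is then told. If the attachment already says this, bring the protocol into line with it.
2. Amend section 9.3 so that the NKF coordinator keeps a de-identified tally of the three event types on the university-hosted PMMS: date, facility code, type, and first or repeat for that mentee. Add a medical-emergency reason to the incomplete-session report if it lacks one. If a log already exists, cite it and route its counts.
3. Send counts to the principal investigator, annually to the DSMB, and into the final report, labelled as uncontrolled and not as evidence of harm. The principal investigator sends to the IRB any event judged unexpected and possibly related.

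The cost is protocol wording, perhaps one form item, and a short log of notices that already reach NKF or the PMMS. The downsides are the lack of a control-arm comparator and a small, sensitive record. It must be held without identifiers, because counts per clinic will be small and section 14.5 notes that NKF is not a HIPAA-covered entity.

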9.3.1 Serious Adverse Events

N/A

9.3.2 Regulatory Reporting for Studies Conducted Under IND

N/A

9.3.3 Regulatory Reporting for Studies Not Conducted Under IND

N/A

9.3.4 Other Adverse Events (if applicable)

N/A

9.3.5 Other Unanticipated Problems

N/A

9.3.6 Reporting of Pregnancy

N/A

9.4 TYPE AND DURATION OF FOLLOW-UP OF SUBJECTS AFTER ADVERSE EVENTS

N/A

9.5 HALTING RULES

N/A

9.6 SAFETY OVERSIGHT

An external data safety monitoring board (DSMB) consisting of 5 members (outside of the University of Michigan) has been identified. The DSMB includes a biostatistician unrelated to the trial, a patient, a nephrologist, and a layperson unrelated to the field (e.g., bioethicist).

The DSMB met in 2021 for orientation to the protocol, and to advise on desired data for reporting. The DSMB will then meet annually during the trial implementation and analysis periods, or more frequently as requested by DSMB members.

The study team will produce interim analyses every year of the trial implementation period, or as requested by the DSMB. We currently anticipate reporting annually to the DSMB blinded data on IDH and mortality rates in each treatment arm. The study has no stopping rules.

10 CLINICAL MONITORING

10.1 SITE MONITORING PLAN

I. Study Governance

FMCNA and NKF will participate in the study in accordance with executed subcontracts. Prior to participation in the study, each facility's Governing Body will review study materials and approve participation.

II. Study Champion

The Medical Director and Clinical Manager at each site with an intervention (n=15; the 5 clinics doing data collection only will not have a Study Champion) will then identify a “Study Champion,” who will ideally be a Clinic Manager or Staff Nurse. Each Study Champion will attend a train-the-trainer session with other Study Champions prior to intervention start at their sites. The Study Champion will speak with a University of Michigan Project Manager at least monthly during the trial in study facilities. The Study Champion’s role will involve:

- Participating in quarterly Operations Committee meetings (to take place during the baseline and intervention periods)
- Serving as a liaison to provide staff feedback to the University of Michigan Project Coordinator(s).
 - Examples: Post a study comments notebook in the break room, accept verbal comments from staff, and convey comments during Operations Committee calls.
- Co-leading with Clinical Manager, discussion about checklist implementation at two staff meetings
- Updating the Research Binder with current patient lists and any other updated documents throughout the study
- Conveying positive messaging about the study

III. Operations Committee

An Operations Committees will be formed in each study facility with an intervention (no Operations Committee will be formed for clinics randomized to data collection only); this Committee will include staff members in authority positions such as the local Clinical Manager and Directors of Operations. The Clinical Manager is accountable for the operation of the facility, has authority over the staff in his or her assigned clinic, and has physical presence in the clinic on a regular basis. The Director of Operations is accountable for a group of clinics in the geographic area, and has authority over the Clinical Manager. The Operations Committee will meet three times over the course of the study, and include the Study Champion as per above, and others selected to represent different organizational levels and perspectives. Patient representatives (n=1-2) will also participate in the Operations Committee and will be selected based on the following criteria:

- 1) Not excluded from the study on the basis of vulnerable status or opting out
- 2) Access to email for receipt of meeting materials
- 3) Sufficient English ability to participate in meetings (English as primary language)
- 4) Sufficient hearing ability to participate in meetings by phone (per patient’s judgement)
- 5) Nomination by Clinic Manager, or self-nomination.

The Operations Committee will oversee intervention implementation in each of the study facilities. At the meetings, the UM Study Coordinator will provide feedback to the facility regarding intervention fidelity (e.g., checklist completion rates, staff training completion rates, patient retention rates across all five peer mentoring sessions). Feedback will be sought from facility staff regarding the intervention, and its impact upon facility operations. The Committee will also engage in collective problem-solving as needed as led by the UM study coordinator, who will schedule, plan, organize and lead Operations Committee meetings.

IV. Role of Medical Director at Study Facilities

In addition, the Medical Director at each site will communicate initial study information to medical colleagues (attending nephrologists and other providers) in the facility, and then communicate as needed to these colleagues throughout the study. In order to increase the appeal of participation, UM has also incorporated a total of \$500 divided into two payments (\$250 each payment) for each of the Medical Directors of study facilities in the project budget for carrying out their responsibilities related to the study as described below. UM will be responsible for managing the payment process. Each payment will be triggered by completion of the Practice Patterns Survey associated with that payment (see attached Practice Patterns Survey - Medical Directors and Practice Patterns Survey - Nurse Managers).

Payment #1 of \$250 shall be compensation for the following activities:

- Participate in the process of Governing Body approval for the study.
- Communication of initial study information to medical colleagues (attending nephrologists and other providers) in the clinic.
- Work with Clinical Manager to identify a Study Champion, if applicable.
- Work with Clinical Manager to identify patients deemed vulnerable that should be excluded from the study, per the study's exclusion criteria.
- Complete the pre-intervention phase Practice Patterns Survey, to be completed during the 12- week baseline data collection period before the intervention phases begins.

Payment #2 of \$250 shall be compensation for the following activities:

- General support of the study and communication as needed to medical colleagues (attending nephrologists and other providers) in the clinic.
- Completion of the post-intervention phase Practice Patterns Survey, to be completed during the 12-week follow-up period following the intervention phase.

V. UM staff monitoring of opt out process

The University of Michigan is responsible for the opt out processes for patients. Under the direction of a UM study coordinator available online via initial enrollment, each patient will be given an information sheet by FMCNA staff. FMCNA staff will distribute the information sheet to patients, and record the date that a patient received the information sheet and the date of any opt outs (as applicable) on an Opt Out Worksheet, adding any new patients missing on the worksheet as needed. The UM study coordinator will be granted an FMCNA secure email address for communications concerning the opt out process and other study matters.

VI. Assessment of Intervention Implementation (Aim 3)

Feasibility Evaluation. The study will involve an initial pilot feasibility assessment for current study procedures. This will involve assessment of metrics concerning:

- (1) availability of a sufficient amount patient dialysis session data to measure the impact of the interventions on the primary outcome (data for 3,600 dialysis sessions for each of the 8 pilot clinics during the pilot intervention period);
- (2) sufficient patient participation in the peer mentoring program (up to 30 patients start peer mentoring in each of the trial period clinics with peer mentoring, and up to 22 patients finish peer mentoring in each of the pilot clinics with peer mentoring); and

(3) sufficient staff participation in the online training sessions (at least 75% of the staff complete at least 90 minutes of training during the first 14-16 weeks of the intervention period in the pilot clinics with the provider intervention).

To assess intervention implementation (Aim 3), monitoring activities will also seek to identify variation in implementation approaches adopted within different study facilities, and to characterize differences in intervention acceptance and workflow integration. These analyses will help with understanding any potential differences in intervention effects between sites, and with identifying and responding to any emergent implementation challenges throughout the trial.

Meeting-based data collection will support study monitoring, and related Aim 3 analyses. Meeting data will be unobtrusively collected in all facilities in which there is an intervention. Specifically, these data collection activities will leverage already-planned project activities; no additional meetings will be planned specifically for this form of data collection. UM researchers will attend the following events which are already planned as part of the trial; no audio or video-recordings will be made of any meetings or sessions:

- Online Staff Training Sessions
 - Staff Training regarding IDH prevention Parts 2 and 3 (14 facilities)
 - Staff Training regarding peer mentoring intervention and tablet management (14 facilities)
- Operations Committee (OC) meetings (15 facilities; the 5 clinics doing data collection only, will not have an Operations Committee)

Online Training Sessions. At the Online Training Sessions, UM researchers will take descriptive field notes.¹⁶¹ Attendees will be informed that notes will be taken, the purpose of the notes, and that comments made during meetings may be tied to a staff member's role but staff names will not be recorded. The attendees will be informed that they can decline to have their comments recorded. The field notes will document:

- staff questions during the sessions;
- staff members' stated reactions to the interventions; and
- discussions in which the staff talk about their plans for, and experience with, integrating the provider intervention into their workflows.

OC meetings. At the OC meetings for each site, the meeting agendas will include a small number of questions directly related to study intervention implementation as provided in this document which UM investigators and/or staff will pose, then recording the answers in descriptive field notes. These questions are directed to FMCNA staff and will be asked after any patient representatives have left the meeting. The questions are as follows:

- At Pre-intervention OC meeting:
 - Staff Intervention Facilities
 - We are planning to train you to use a checklist to identify patients at risk of intradialytic hypotension. The checklist will rely on information from the fluid management tab. Is there anything that we should consider about how you use the fluid management tab now that we should take into account in planning your training?
- At the two OC meetings during intervention period:
 - Staff Intervention Facilities:
 - Your facility has been given a checklist to use to identify patients at

increased risk of IDH. Please tell us about how you are using the checklist.

- *Follow-up questions as needed:*
 - Who is completing the checklist?
 - When are they completing the checklist?
 - What do they do before completing the checklist?
 - What do they do after completing the checklist?
- What is working well about using the checklist?
- Are there things that are not working well with using the checklist? If so, what are they?
- Patient Intervention Facilities:
 - Some patients at your facility have been given tablet computers for patients to use at home to obtain peer mentoring and education about IDH prevention.
 - *Follow-up questions as needed:*
 - Have patients brought their tablet computers into the clinic? If so, please tell us what happened.
 - Have patients talked to any of you about anything regarding tablet use?
 - Have you noticed any changes in topics that patients are bringing up in their appointments with you?
 - Has anyone started to record things at home and bring in data and do you have reason to believe it's because of the intervention?
 - Have you noticed patients talking to each other about the intervention?

VII. Surveys

A Practice Patterns survey will be completed by the Medical Director and Clinical Manager prior to, and after the intervention period. The survey will document fluid management practices used in each facility, including the no-intervention (usual care) sites.

A patient satisfaction survey will be given by the NKF to patients after they complete the patient activation intervention. Results will be monitored in order to identify patient experiences with the multimedia educational modules and peer mentoring intervention. Aggregate results will be shared with NKF so that any necessary program adjustments can be made.

A peer mentor satisfaction survey will be given by the NKF to peer mentors to assess their experiences with the study's digital tools, training, and support. Aggregate results will be shared with NKF so that any necessary program adjustments can be made.

VIII. Monitoring by Study Team

The study team will conduct scheduled assessments of study recruitment, data integrity and quality, withdrawals, and compliance with protocol plan on a monthly basis. This information will be reported at the monthly project Steering Committee meetings.

